7.1.7 Excluded Treatments, Medical Devices, and/or Procedures During Study Period

Concomitant treatment with **up to 2** oral migraine preventive medication is allowed under the following conditions:

- (1) drug regimen (ie, formulation, frequency of use, dose) is stable ≥ 2 months prior to baseline period start
- (2) drug regimen is at generally accepted dose, frequency and route for its use in migraine
- (3) drug regimen is not anticipated to change during baseline period or postrandomization (ie, during the subject's study participation).

Examples of such medications include but are not limited to the following:

- Antiepileptics (eg, divalproex sodium, sodium valproate, topiramate, carbamazepine, levetiracetam).
- Angiotensin receptor blockers (eg, candesartan) or ACE inhibitors (eg, lisinopril).
- Beta blockers.
- Calcium channel blockers (verapamil, amlodipine, cinnarizine, lomerizine) or calcium antagonists (eg, flunarizine).
- Tricyclic antidepressants.
- Other antidepressants (eg, serotonin-norepinephrine reuptake inhibitors, selective serotonin-reuptake inhibitors).
- Other drugs used for migraine prevention (eg, **coenzyme Q10**, clonidine, guanfacine, methysergide, cyproheptadine, pizotifen, butterbur, feverfew, magnesium (≥ 500 mg/day), riboflavin (≥ 100 mg/day)).

Approved

Prohibited Medications	Time Period for Exclusion
Concurrent use of non-investigational anti-CGRP mAbs	Prior history of treatment with and throughout the study
Use of the following acute medications for the acute treatment of migraine: Barbiturates or butalbital-containing medication for > 4 days/month Short-acting opioids or short-acting opioid-containing medication for >15 days/month Long-acting opioids or long-acting opioid-containing medication Cannabidiol (CBD)-containing products anticipated to have a systemic effect (eg, ingested or inhaled products) > 4 days/month	2 months before the start of the screening period and throughout the study
Investigational medications	30 days or 5 half-lives before the start of the screening period and throughout the study
Botulinum toxin (in the head and/or neck region)	4 months before the start of the screening period and throughout the study
Prohibited Procedures or Devices	Time Period for Exclusion
For any indication Infusion rescue therapy (ie, steroids, valproate sodium, dihydroergotamine) Note: infusion rescue therapy may be allowed during DBTP if medically justified	During screening period or baseline period

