9.6 Safety Analyses

9.6.1 Analyses of Primary Safety Endpoint(s)

For safety endpoints **during the DBTP**, all randomized subjects who received at least one dose of investigational product (ie, Safety Analysis Set) will be analyzed based on

the randomized treatment unless a subject has received the incorrect dose during the entire period of interest (treatment period or study). Safety analyses will be repeated for the non-opioid treated cohort, opioid-treated cohort, and overall. For safety analyses of **vital signs** in OLTP, descriptive summaries of **change from baseline values** will be tabulated based on observed data using pre-OLTP baseline.

No statistical testing comparing treatment groups will be performed in the safety analyses.

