9.6.3 Vital Signs

The analyses of vital signs (systolic/diastolic blood pressure (SBP/DBP), **and heart rate**) will include summary statistics of change from baseline over time by treatment group.

Subject incidence at each time-point within the following defined categories for each treatment period:

- Increase from baseline ≥ 10 mmHg in DBP with DBP > 90 mmHg
- Increase from baseline ≥ 10 mmHg in DBP with DBP ≤ 90 mmHg
- Increase from baseline ≥ 20 mmHg in SBP with SBP > 140 mmHg
- Increase from baseline ≥ 20 mmHg in SBP with SBP ≤ 140 mmHg
- Change from baseline in heart rate of ≥ 15 bpm (increase) or heart rate ≥ 120 bpm
- Change from baseline in heart rate of ≤ -15 bpm (decrease) or heart rate ≤ 50 bpm

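### Each heart-rate safety category merges a change criterion and a level criterion, so pre-existing and new values share one row and cannot be told apart

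*SAP*

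**What the plan says.** SAP 9.6.3 lists six vital-sign categories, to be reported as "Subject incidence at each time-point within the following defined categories for each treatment period". Two concern heart rate:

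- High: "Change from baseline in heart rate of ≥ 15 bpm (increase) or heart rate ≥ 120 bpm"
- Low: "Change from baseline in heart rate of ≤ -15 bpm (decrease) or heart rate ≤ 50 bpm"

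Neither asks what the rate was at baseline when the level part is applied.

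The four blood-pressure categories are built differently. "Increase from baseline ≥ 10 mmHg in DBP with DBP > 90 mmHg" is paired with a row for the same rise ending at or below 90 mmHg, and "Increase from baseline ≥ 20 mmHg in SBP with SBP > 140 mmHg" with a row for the same rise ending at or below 140 mmHg.

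The same section says the vital-sign analyses "will include summary statistics of change from baseline over time by treatment group", and heart rate is included. SAP 9.6.1 adds that "No statistical testing comparing treatment groups will be performed in the safety analyses", and that vital signs in the open-label period are summarised against the pre-OLTP baseline. Table 5-7 gives six post-baseline vital-sign visits in the double-blind period (weeks 4 to 24) and two in the open-label period (weeks 40 and 52).

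**The concern.** Vital signs are one of the two safety endpoints named in Protocol 4.1 and SAP 2.1; the other is adverse events. With no safety testing, the reader depends on the descriptive counts. A heart-rate row that can be entered either by changing or by being at a level does not tell the reader which happened. It counts people whose rate never moved, and it puts a rise from 60 to 75 bpm beside a rate of 120 bpm.

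Low rates at entry are plausible in this population. "Beta blockers" are among the allowed oral preventives in Protocol 7.1.7, and the eligibility criteria in Protocol 6.1 to 6.4 set no heart-rate limit.

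**Working it through.** **Logic of the definitions (no assumptions needed).** The low row is met if change ≤ −15 or rate ≤ 50.

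- Baseline 48, visit 48: change 0, rate ≤ 50. Counted, at up to 6 double-blind and 2 open-label visits.
- Baseline 85, visit 70: change −15, rate above 50. Counted in the same row.
- Baseline 60, visit 75: change +15. Counted in the high row, alongside anyone at 120 bpm or more.

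In the blood-pressure rows nobody is counted without a rise, and the level only decides which of two rows the rise falls in. In the heart-rate rows a subject can be counted without any change, and subjects who changed are not split by level.

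**Illustration of size.** The plan states no heart-rate incidence or variability, so there is no figure to reproduce. The inputs below are assumptions, not document values: mean 68, 72 or 76 bpm; between-subject SD 9 or 11; SD of the baseline-to-visit difference 6, 8, 10 or 12; no drug effect. Baseline and visit are bivariate normal, rounded to whole bpm, with correlation ρ = 1 − SD_diff² / (2 × SD²). For SD 11 and SD_diff 10, ρ = 1 − 100/242 = 0.59. There were 24 scenarios with 4 million simulated subjects each. Five of them:

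| Mean / SD / SD_diff | ρ | Low row flagged | of these: change only, rate > 50 | of these: level only, no 15-bpm fall | of these: ≤ 50 at both times, no 15-bpm fall | High row flagged |
|---|---|---|---|---|---|---|
| 76 / 9 / 6 | 0.78 | 1.00% | 77% | 22% | 6% | 0.79% |
| 68 / 11 / 6 | 0.85 | 6.21% | 10% | 87% | 51% | 0.79% |
| 72 / 11 / 10 | 0.59 | 9.05% | 72% | 19% | 7% | 7.37% |
| 76 / 9 / 12 | 0.11 | 11.39% | 98% | 0% | 0% | 11.33% |
| 68 / 11 / 12 | 0.40 | 14.42% | 61% | 21% | 8% | 11.34% |

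The fourth-to-last and third-to-last columns, with the few subjects who meet both criteria, make up the low row; the ≤ 50 at both times column is part of the level-only column.

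Over all 24 scenarios, per visit:

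- Low row: 1.0–14.4%. With 183 planned per arm in the nonopioid cohort (SAP 3.2), 0.0100 × 183 ≈ 2 to 0.1442 × 183 ≈ 26 subjects. Change-only subjects are 10–98% of those flagged.
- High row: 0.79–11.37%, that is 0.0079 × 183 ≈ 1 to 0.1137 × 183 ≈ 21 subjects. At least 99.5% are change-only with a rate below 120 bpm. This leans on the normal tail, which almost never reaches 120 bpm under these means and SDs.

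**What an *and* rule would do.** In the same simulation the low row falls to about 0.02–2.5%, and the high row to under 0.01%, almost empty.

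**The case against.** The case for leaving the table alone has several sound parts.

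- *The blood-pressure rows also count every rise, whatever the level.* True: the rows are complementary pairs. They are therefore no precedent for requiring change and level together for heart rate. They do keep the two pieces of information apart, which the heart-rate rows do not.
- *A heart-rate signal can still be seen.* A reader might infer that the plan cannot show one. The documents do not support that. Change from baseline is summarised by arm and visit, and SAP 9.1 includes quartiles, minimum and maximum for continuous endpoints. Under Protocol Appendix 4, vital-sign abnormalities that the investigator judges clinically significant are adverse events, and these are tabulated by arm. None of this gives the number of subjects reaching 50 or 120 bpm.
- *The arms are not biased.* A reader might infer a distorted comparison. In the double-blind period treatment is randomised against placebo, and in the nonopioid cohort randomisation is stratified by concomitant oral preventive use (Protocol 7.2). Allowed preventive regimens must also be stable (Protocol 7.1.7). Pre-existing low rates should be balanced, so they add a common background and no more. This answer does not carry over to the open-label period.
- *An unchanged low rate is not labelled a decrease.* In the SAP's wording the bracketed term belongs to the change part only. Such a subject enters the combined category; the plan does not call it a fall in rate, or an event.

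**Conclusion.** The point holds as a matter of tabulation. The combined rows count unchanged low or high rates together with changes, and the number reaching the level thresholds cannot be recovered from them or from any other planned table. In the double-blind period the effect is dilution; in the open-label period the counts may describe only what subjects brought with them. This is a minor, inexpensive improvement to a descriptive table and touches no efficacy result or error rate.

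A reader might also infer that ordinary 15-bpm variation swamps the clinically extreme rates. The documents give no variability from which to judge that. In the assumed scenarios it is so for the high row throughout, but for the low row the balance runs from 98% change-only to 87% level-only depending on the mean and the SDs. Only the mixing is established, not which part dominates.

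**What to change.** In SAP 9.6.3, keep the thresholds as they stand and replace each combined heart-rate row with two:

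1. change from baseline of at least 15 bpm in the stated direction;
2. heart rate at or beyond the stated level (120 or 50 bpm), limited to subjects who did not meet that level at baseline, or split by whether they did.

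State that the baseline condition uses the same baseline as the change row for that period, which under SAP 9.6.1 is the pre-OLTP baseline in the open-label period. Do not simply replace *or* with *and*: without a complementary row this would nearly empty the high category and would drop, for example, a subject going from 118 to 125 bpm.

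The cost is a change to two derived flags and two extra table rows (more if the level rows are split by baseline status rather than limited). No new data are collected.

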9.6.4 Exposure to Investigational Product

Descriptive statistics will be produced to describe the exposure to investigational product by treatment group and treatment period. The number and percentage of subjects with dose change, reason for dose change and duration of exposure to investigational product in days will be summarized by treatment group.

9.6.5 Exposure to Concomitant Medication

The number and proportion of subjects receiving acute headache medications will be summarized by acute headache medication category for each treatment group.

9.7 Other Analyses

9.7.1 Analyses of Health Economic Endpoints

Health Resource Utilization Questionnaire (HRU)

The questionnaire is designed to collect data on HRU. Specifically, the aim is to capture frequency of **headache**-related hospitalizations and outpatient visits including emergency department visits, urgent care visits, and other clinical visits. The recall period for the HRU questionnaire is 24 weeks, and the HRU questionnaire will be administered on day 1, and week 24 of the DBTP. The questionnaire assessed at the early termination visit before week 24 should only include HRU recalled since the previous assessment at day 1 to avoid collecting duplicate information.

10. Changes From Protocol-specified Analyses

During the development of SAP amendment, it was realized that there are protocol-specified analyses that cannot be implemented/performed and the

protocol is not required to be amended. Ditans is included in the list of acute headache medications in Section 5.1. The definition of efficacy analysis set stated in the protocol is not applicable to all efficacy endpoints and has been corrected in Section 6.2 to what was intended. These changes will also be documented in the clinical study report.

11. Literature Citations / References

Quade, D. (1966), Rank analysis of covariance, University of North Carolina, Institute of Statistics Mimeo Series. No 483.

12. Data Not Covered by This Plan

There are no plans to specifically analyze or summarize the following data points.

- Data for biomarker development
- Data from the optional interview-based substudy

13. Appendices

Not applicable
